1.4 Sample Size Estimates

The planned sample size for each pairwise comparison is 1,000 participants (500 participants in each group). The sample size is sufficient to detect a recovery rate ratio (RRR) of 1.25 for time to sustained recovery with 90% power, using a one-sided test with a significance level of 0.025. The treatment groups are compared using Gray's test with ρ =0, the competing risks analogue of the log-rank test.

Sample size calculations are described in detail in Section 6.3 of the protocol.

Blinded sample size re-estimation will be carried out before enrollment is complete to determine whether the planned sample size of 1,000 participants followed for 90 days will yield the planned number of 843 primary events. The blinded sample size re-estimation does not involve unblinding of the treatment difference. It will be based on the pooled outcome data. Sample size may be increased to achieve the event target in the planned follow-up of 90 days. A

sample size increase may also be considered in order to achieve the event target before all participants are followed for 90 days.

When 300 participants (150 per study arm) are enrolled and have Day 5 outcome data, an early futility assessment is planned. This assessment will be based on two ordinal outcomes, denoted as "pulmonary" and the "pulmonary+"; both are ordered categorical outcomes with 7 categories, assessed on Day 5 (the two outcomes are described in Appendix A). Treatment groups will be compared using proportional odds models. With 300 participants, the early futility assessment is powered to detect a summary OR=1.60 with power of 95%, using a one-sided test with significance level of 0.30.¹ Given the two-outcome decision rules, an investigational agent with a summary OR=1.60 at Day 5 for both outcomes, would pass the futility assessment with a power between 93% and 98%, and a type I error between 0.21 and 0.39.

2 Interim DSMB Reviews: Goals and Format

Each investigational agent versus control will be reviewed as a separate clinical trial; separate data reports will be prepared for each investigational agent and the corresponding randomized (pooled) placebo group.

Goals of the interim reviews:

- Protect the safety of study participants.
- Advise on stopping or modifying the trial for efficacy, for patient safety in case of emerging data on harm, or for futility.

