For **binary outcomes**, probabilities will be compared between the investigational agent and its control group using Cochran-Mantel-Haenszel tests (CMH) or logistic regression. If the numbers are sufficiently large, CMH tests will be stratified according to the planned randomization strata (disease severity and site pharmacy), as described above under "stratification". Odds ratios (OR) with 2-sided 95% confidence intervals (CI) will be estimated using logistic regression models.

For longitudinally measured binary outcomes, the treatment effect through follow-up will be estimated with 95% confidence intervals using generalized estimating equations (GEE) with a logit link function; the treatment effect is estimated via the interaction between the indicator for treatment group and the indicator for follow-up (versus baseline) visits. When there is more than one follow-up visit, "visit number" (day) may be included as categorical variable in the model, for variance reduction; alternatively, "time" may be included as a continuous variable.

Ordered categorical outcomes (pulmonary and pulmonary+) will be compared between treatment groups using proportional odds models, and the summary OR will be estimated with a 2-sided 95% CI.² Additionally, to aid the interpretation, the ordinal outcome will be dichotomized according to cumulative probabilities of the ordered categories, comparing treatment groups for proportions of participants in category 1, in the "best 2 categories", "best 3 categories", etc.; these comparisons will be performed using logistic regression (or stratified CMH tests).

For interim analyses of the ordinal outcomes, if one or more recently enrolled participants have died (i.e., their outcome status is known) but their current administrative follow-up has not yet reached the time point at which the treatment groups are to be compared (e.g., day 5), analyses will be restricted to participants with administrative follow-up greater or equal to the target time point.

Models will be adjusted for the baseline categories of the pulmonary+ outcome and for study pharmacy, by including the corresponding indicator variables in the model.

- If the number of observations is too small to adjust for both categorical covariates, preference will be given to the adjustment for the pulmonary+ category at baseline. Site pharmacy categories may be collapsed as described above under "stratification".

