- For the initial futility analysis (after 150 participants per arm have Day 5 data), the adjustment for the pulmonary+ categories and pharmacy will be additive.
- For key analyses, unadjusted OR estimates will also be provided as sensitivity analyses.

The validity of the proportional odds assumption will be assessed by testing for heterogeneity in the log ORs (for the treatment effect) across the dichotomized cumulative ordered categories in the corresponding logistic regression model (partial proportional odds model, test for "unequal slopes").

• The primary sensitivity analysis testing the proportional odds assumption will compare the unadjusted proportional odds model for the treatment comparison (null model) versus a partial proportional odds model that allows for "unequal slopes" across the dichotomized cumulative categories (i.e., when testing the proportional odds assumption for the treatment comparison with respect to the pulmonary outcome on Day 5, the model will allow for heterogeneous ORs across the Day 5 pulmonary categories) as well as

across the stratification covariates (i.e., the baseline pulmonary+ categories and site pharmacy strata) (full partial proportional odds model).

Continuous outcomes will be compared between treatment groups using ANCOVA models for comparing means, if the ANCOVA model assumptions hold. If the distributions of the continuous outcomes are skewed, outcomes may be transformed, or compared between treatment groups using rank-based methods, such as the Wilcoxon test, or quantile (median) regression.

Comparisons between treatment groups for a continuous outcome will be adjusted for baseline values of the outcome, for the purpose of variance reduction, unless there are concerns over model stability with such an adjustment. For this purpose, the baseline value will be included as covariate in the model (e.g., ANCOVA, linear mixed models).

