 - If Day 5 data are missing for a substantial proportion of participants (e.g., more than 5% of the mITT cohort), multiple imputation will be used to impute missing Day 5 data for the pulmonary and pulmonary+ outcomes. For the imputation, the following baseline covariates will be considered in addition to the indicator for treatment group: age, sex, country, duration of symptoms prior to enrollment, status of the ordinal pulmonary (or pulmonary+) outcome, and presence of comorbidities. Ten rounds of imputation will be used to estimate the summary odds ratio.
 - The number and proportion of participants with missing data will be reported.

Sensitivity analyses

- As sensitivity analyses, the treatment groups will be compared by **modified intentionto-treat (mITT)** after excluding participants who did not receive any of the assigned investigational agent (active or control). This mITT analysis will be provided at important decision points, e.g., when the test statistic approaches the monitoring boundary, and for the final analyses after completion of the trial.
- Treatment groups will be compared for the pulmonary and pulmonary+ outcomes on Days 1-7, to monitor the consistency of the treatment effect over time.

Assessment of model assumptions

- For the pulmonary and pulmonary+ outcomes at Day 5, the proportionality assumption
 of the odds ratio will be assessed (by including the interaction between the treatment
 group indicator and indicators for the Day 5 cumulative ordinal categories in the model,
 as well as the interactions between the treatment group indicator and the indicators for
 the strata by baseline pulmonary+ categories and site pharmacy; this corresponds to
 testing for separate slopes using a partial proportional odds model, see section 3 under
 "ordered categories"). If there is evidence for non-proportionality, the summary odds
 ratio in the proportional odds model will still be used to quantify the treatment effect, and
 the analyses of the dichotomized ordinal outcome categories will be used to help
 interpret the treatment effect.

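### The proportional-odds check in SAP section 3 puts baseline and pharmacy terms in only one of its two models, so prognostic baseline severity can be mistaken for non-proportionality

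*SAP*

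**What the plan says.** SAP section 3 (ordered categorical outcomes) states the aim of the check as "testing for heterogeneity in the log ORs (for the treatment effect) across the dichotomized cumulative ordered categories". That concerns one thing: whether the treatment odds ratio is the same at every cut-point.

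The bullet that follows defines the main check. It "will compare the unadjusted proportional odds model for the treatment comparison (null model", and the alternative is a partial proportional-odds model with unequal slopes over the Day 5 categories and also "across the stratification covariates (i.e., the baseline pulmonary+ categories and site pharmacy strata) (full partial proportional odds model". The covariates are named only for the alternative.

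The null is not the model used for the treatment comparison. For that, section 3 says: "Models will be adjusted for the baseline categories of the pulmonary+ outcome and for study pharmacy". Section 10.2.2 likewise makes the adjusted model primary for the early futility review.

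Section 10.2.2 (assessment of model assumptions) describes the check again. It adds interactions of treatment with the Day 5 cut-points, "as well as the interactions between the treatment group indicator and the indicators for" the baseline and pharmacy strata. It refers back to section 3 but does not name the null model. If non-proportionality is found, the summary odds "ratio in the proportional odds model will still be used to quantify the treatment effect", and the dichotomised analyses help to interpret it.

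**The concern.** A test of an assumption should compare two models that differ only by that assumption. Here they can also differ by the prognostic effect of baseline severity, the prognostic effect of pharmacy, and any treatment-by-stratum heterogeneity. A rejection cannot then be attributed to non-proportional treatment effects.

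Some prognostic effect is plausible. In disease severity stratum 1 the baseline covariate is an oxygen-requirement category on the same kind of scale as the outcome, measured five days earlier. The SAP prefers it over pharmacy when data are sparse (section 3), and section 13.2 uses the baseline Pulmonary category to predict Day 5 status.

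Two things are at stake. A false signal would send readers to the dichotomised odds ratios, which section 10.2.2 itself says are not adjusted for multiplicity. And a check that rejects for other reasons cannot identify genuine non-proportionality. Section 8.3 refers to the section 3 methods for Days 1-7, 14 and 28, so the problem is not confined to the futility review.

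**Working it through.** **Inputs from the SAP.** Sample size, section 1.4: "When 300 participants (150 per study arm) are enrolled and have Day 5 outcome data". Seven outcome categories (section 1.4), hence six cut-points. Three baseline categories in stratum 1 (section 10.2.2). Default significance at p ≤ 0.05 (section 3); no level or test statistic is given for this check.

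**Assumptions.** Likelihood-ratio test at 0.05. Baseline mix 25/40/35%. Day 5 mix in the middle baseline category 25/25/18/12/12/5/3%. Prognostic odds ratio per baseline category varied from 1.0 to 3.0. No pharmacy effect. Proportional odds exactly true given baseline.

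**Step 1: the plan's own figure.** The SAP gives none for the check. The nearest is in section 1.4: "the early futility assessment is powered to detect a summary OR=1.60 with power of 95%, using a one-sided test with significance level of 0.30". Whitehead's formula is power = Φ(√(N × (ln OR)² × s / 12) − z₀.₇₀), with s = 1 − Σp³. Here 300 × 0.2209 / 12 = 5.52. With s = 0.852, √(5.52 × 0.852) = 2.169, and 2.169 − 0.524 = 1.645, giving 95.0%. The control distribution is not in the text supplied. Over s = 0.75 to 0.98, power is 93.5% to 96.4%, so the figure reproduces. The Day 5 mix assumed above has s = 0.959, inside that range.

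**Step 2: what the two models differ by.** Leaving pharmacy out, the unadjusted null has 6 intercepts + 1 treatment slope = 7 parameters. The full partial model over 2 arms × 3 baseline categories has 6 × 6 = 36. The difference of 29 degrees of freedom splits as follows:
- baseline main effects: 2
- treatment-by-baseline: 2
- unequal treatment slopes: 5
- unequal baseline slopes: 10
- unequal interaction slopes: 10

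Only 5 of the 29 correspond to the stated aim.

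**Step 3: false rejection.** 200 simulated trials per scenario, N = 300. Each entry is for treatment OR 1.0 / 1.6.

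| Prognostic OR per category | Section 3 as written | Baseline main effects in both models, same full alternative | Treatment-by-baseline added to adjusted model |
|---|---|---|---|
| 1.0 | 7.5% / 12% | 7.5% / 13.5% | 8.5% / 2% |
| 1.25 | 17.5% / 18% | 11% / 10% | 5% / 4% |
| 1.5 | 37% / 43.5% | 8% / 8.5% | 5% / 3% |
| 2.0 | 89% / 85.5% | 8% / 10.5% | 4% / 4.5% |
| 3.0 | 100% / 99.5% | 10% / 7% | 5.5% / 5% |

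Simulation error is about ±3 points near 5% (1.96 × √(0.05 × 0.95 / 200) = 0.03) and ±7 points near 50% (1.96 × √(0.25 / 200) = 0.07). A separate simulation of the section 3 comparison gave about 10%, 34%, 84% and 100% at prognostic odds ratios of 1, 1.5, 2 and 3, against 7-10% with baseline main effects in both models.

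**Step 4: other readings.** If section 3 means treatment-by-baseline terms added to the unadjusted model without main effects, rejection at a prognostic OR of 2.0 is 92.5% / 90%, so the defect remains. If section 10.2.2 means interactions added to the adjusted model, the last column applies: 3-5.5% for prognostic ORs from 1.25 to 3.0, with no rise. On that reading, however, real treatment-by-stratum heterogeneity would be labelled non-proportionality.

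**Step 5: the source of the excess.** Once both models share the baseline main effects, rejection no longer rises with prognosis. What remains above 5% also appears with no prognosis at all, which points to sparse cells. A treatment-slopes-only test (unadjusted, 5 df) rejected in 3.5-9%. The adjusted version recommended below was not simulated.

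**The case against.** The strongest reply is that nothing decisive hangs on this check. The futility guidelines in section 10.2.1 use one-sided p-values against 0.30, which section 10.2.2 takes from the adjusted model. The summary odds ratio is kept after a rejection. The dichotomised analyses are produced anyway, with a caution about multiplicity. The listed contents of the summary reports do not include this test. All of that stands. A reader might infer that a rejection replaces the summary odds ratio with the dichotomised outcomes, or that the DSMB would be told at the futility decision that the model fails. The documents do not say either.

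A reader might also infer that the check rejects whenever baseline is prognostic. It does not: at an odds ratio of 1.25 per category, rejection is about 18%. The SAP gives no prognostic strength, so the high rates depend on an assumed input.

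Nor is section 10.2.2 simply the same error repeated, because it can be read as building on the adjusted model. And the SAP names no test statistic: a test of the treatment slopes alone, within the partial model, would match the stated aim and would not be expected to respond to prognosis. But the section 3 bullet describes a comparison of two whole models and names the unadjusted one as null, and section 10.2.2 points back to it.

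Finally, the adjusted model also assumes proportional odds for its covariates, so a wider check has a legitimate use. It should be reported separately from the check on treatment.

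**Conclusion.** The point holds for section 3 as worded, assuming a likelihood-ratio test at 0.05. The comparison confounds prognosis with non-proportionality. With 300 participants and proportional odds exactly true, false rejection is about 18% at a prognostic odds ratio of 1.25 per baseline category, 34-44% at 1.5, 84-89% at 2 and about 100% at 3. The figures rest on the assumed baseline and Day 5 distributions, leave pharmacy out, and represent the alternative by the saturated treatment-by-baseline model.

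The consequence is confined to interpretation of the ordinal treatment effect. No estimate and no futility rule changes. It is still worth correcting: the specified diagnostic can give the wrong answer, sections 3 and 10.2.2 do not describe the same test, and section 10.2.2 lets the result shape how the effect is read.

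**What to change.** In section 3, make the null the adjusted primary model: treatment, baseline pulmonary+ category and pharmacy, with pharmacies pooled as that section already allows. Make the alternative the same model with only the treatment coefficient free across cut-points. With seven occupied categories this is 6 − 1 = 5 degrees of freedom, and fewer if a category is empty. Name the test statistic and its level.

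Report treatment-by-stratum heterogeneity as a separate test, and covariate non-proportionality as another if it is wanted. Reword section 10.2.2 to describe the same check and name the same null.

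The cost is a few sentences in the SAP and a changed model call. No additional data are needed.
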